**Figure 1: Study Schema**

Histologically confirmed diagnosis of GIST. Patients must have progressed on or be intolerant to imatinib treatment.

Patients will be treated until they develop progressive disease per modified RECIST, experience unacceptable toxicity, or withdraw consent. At the time of progressive disease per modified RECIST, based on independent radiologic review, patients on DCC-2618 or sunitinib will discontinue study drug treatment.

Sunitinib dose modifications are allowed per approved package insert or institutional guidelines. Every effort should be made to continue patients on the initial regimen throughout the first cycle, unless toxicity mandates dose modification. PK-guided dosing is not allowed.

**Table 1: Schedule of Assessments**

Assessments / Procedure 	Screening 	Cycle 1			Cycle 2		Cycles ≥3		EOT Visit (within 7 days after last dose)	Safety Follow Up 30 Days Post Last Dose (+5 days)	Overall Survival Follow Up  (every 3 months ±1 month)
		1 (Baseline)	15 (±1 day)	29 (±1 day)	1 (±3 days)	29 (±3 days)	1 (±3 days)	29 (±3 days)			
Site Visit	X	X	X	X	X	X	X		X		
Remote Questionnaire Completion 								X 			
Phone Call										X	X
Informed Consent	X										
Inclusion/Exclusion Criteria	X										
Medical and Cancer History	X										
Prior Medications/Procedures 	X										
Pregnancy Test 	X	X			X		X		X		
Randomization 		X									
Clinical Laboratory Tests											
Hematology	X	X	X	X	X	X	X		X		
Serum Chemistries	X	X	X	X	X	X	X		X		
Coagulation 	X	X	X 	X	X	X	X		X		
Urinalysis	X	X			X		X 		X		
TSH, Total T3 and Total T4	X	X					X 		X		
Physical Examination	X	Examinations will be driven by clinical findings and/or patient complaints									
ECOG PS 	X	X	X	X	X	X	X		X		
Vital Signs and weight 	X	X	X	X	X	X	X		X		
Height	X										
12-lead ECG 	X	X			X		X		X		
Echocardiogram/MUGA 	X						X 		X		
Dermatologic Examination 	X						X 		X		
Adverse Event Reporting		Continuous from signing informed consent through safety follow up									
Concomitant Medications/Procedures		Continuous from on or after the first dose of study drug through safety follow up									

Assessments / Procedure 	Screening 	Cycle 1			Cycle 2		Cycles ≥3		EOT Visit (within 7 days after last dose)	Safety Follow Up  30 Days Post Last Dose (+5 days)	Overall Survival Follow Up  (every 3 months ±1 month)
		1 (Baseline)	15 (±1 day)	29 (±1 day)	1 (±3 days)	29 (±3 days)	1 (±3 days)	29 (±3 days)			
EORTC QLQ-C30 	X	X	X	X	X	X	X	X	X		
EQ-5D-5L 		X	X	X	X	X	X	X	X		
Healthcare Utilization		X			X		X		X		
PRO-CTCAE Questions 46 and 47 		X	X	X	X	X	X	X	X		
GP5 questions from FACT-G 	X	X	X	X	X	X	X	X	X		
DLQI 	X	X	X	X	X	X	X	X	X		
Study Drug Administration 		X	X	X	X	X	X	X			
Study Drug Dispensation		X			X		X				
PK Sampling 		X	X		X		X 		X		
Pharmacogenomics 		X									
Molecular pathology report with identified KIT/PDGFRA mutation status 	X										
████████████████████	█										
Optional Tumor Biopsy 									X		
Radiologic Imaging 	X				X		X		X		
████████████████████		█					█		█		

CT=computed tomography; ECG=electrocardiogram; ECOG= Eastern Cooperative Oncology Group; EOT=End of treatment; EORTC QLQ-C30=European Organisation for Research and Treatment of Cancer Quality of Life Questionnaire for Cancer 30-item; EQ-5D-5L= EuroQol 5-Dimension 5-Level; DLQI= Dermatology Life Quality Index; MRI=magnetic resonance imaging, MUGA=multigated acquisition; PD=pharmacodynamic; PK=pharmacokinetic; PS=performance status

1. All assessments must be performed predose and within the visit specified windows, unless otherwise described. Additional unscheduled safety or efficacy assessments may be performed at any time as clinically indicated to determine the relevance of specific findings and/or the duration of events.
2. Screening must occur within 28 days prior to the first dose of study drug.
3. All patients will be followed until withdrawal of consent or death from any cause. After the Safety Follow-Up Visit, patients will be contacted every 3 months (±1 month) to collect long-term survival data including OS and PFS2 (i.e. next line of therapy, start date of next line of therapy, date of progression on the next line of therapy).
4. Any medication or non-drug therapy taken, or procedure performed within 30 days prior to screening and before the first dose of study drug.
5. A serum pregnancy test will be performed for females of child-bearing potential by a central laboratory at screening. Urine pregnancy tests will be performed at all subsequent Day 1 visits of each cycle and the EOT visit. Local serum pregnancy test may be performed instead of urine, if it is the standard practice of the site and results are received prior to the patient being dosed in the clinic.
6. Randomization may occur on Day -1. Patients scheduled for Cycle 1 Day 1 on Monday may be randomized on the preceding Friday.

7. Patients taking anticoagulants will also have a test at Cycle 1 Day 15. Monitoring of coagulation tests must be increased for as long as deemed clinically appropriate following a change in anticoagulant dose during the study.
8. Urinalysis testing will be performed by the central laboratory at screening, on Day 1 of Cycles 1, 2, 3 and 4, and the EOT visit and as clinically indicated. If any result is abnormal, a microscopic analysis will be performed by the central laboratory.
9. TSH, Total T3 and Total T4 testing will be performed at screening, on Day 1 of Cycle 1, Day 1 of every odd-numbered cycle (i.e. Cycle 3, Cycle 5, Cycle 7 etc.), and the EOT visit.
10. ECOG PS may be performed pre- or post-dose.
11. Vital sign measurements will be collected after the patient has been at rest (seated or supine position) for at least 5 minutes.
12. All 12-lead ECGs will be performed after the patient has been at rest (supine or semi-recumbent position) for at least 15 minutes. The rest period begins after the placement of the ECG leads.
13. An echocardiogram or MUGA will be performed at screening, Cycle 3 Day 1, and Day 1 of every third cycle thereafter (i.e. Cycle 6, 9, 12, etc.), and the EOT visit, unless deemed clinically appropriate at other times. The same modality (echocardiogram or MUGA) must be used throughout the study. Echocardiogram or MUGA performed as standard of care prior to informed consent may be used as the screening assessment as long as the echocardiogram or MUGA was performed within 28 days prior to the first dose of study drug.
14. All patients will be assessed by a consulting dermatologist at screening for skin lesions, especially for squamous cell carcinoma, actinic keratosis, and keratoacanthomas, within 21 days prior to Cycle 1 Day 1 (baseline). Subsequently, patients will be assessed at Cycle 3 Day 1, Day 1 of every third cycle thereafter (i.e. Cycle 6, 9, 12, etc.), the EOT visit and as otherwise clinically indicated. Dermatological exam that meets the protocol criteria that was performed as standard of care prior to informed consent may be used as the screening assessment as long as the exam was performed within 21 days prior to the first dose of study drug. Dermatological examinations during the treatment phase may be performed up to 7 days prior to the corresponding study visit or post dose on the day of the study visit. See Section 6.11.6 for further details.
15. The EORTC QLQ-C30, EQ-5D-5L, DLQI, GP5 question from FACT-G, and PRO-CTCAE Questions 46 and 47 must be performed before the patient is evaluated by the Investigator or designee on the day of the scheduled visit. If the dermatologic examination or imaging assessments are completed within 7 days of the scheduled visit and the patient is not evaluated by the Investigator or designee, the questionnaires do not need to be completed on that day. The GP5 question from FACT-G will be completed first followed by EORTC-QLQ-C30, DLQI, EQ-5D-5L and PRO-CTCAE Questions 46 and 47. The questionnaires will be collected via an electronic patient reported outcome system. Patients will complete all questionnaires at home on Day 29 of Cycle 3 and beyond via the electronic patient report outcome system. Patient-entered data will not be modified by the Investigator or site staff, ePRO vendor, CRO or Sponsor.
16. On days of study visits, patients will be informed to take the study drug at the study site after predose assessments are completed. See Section 5.3 for dosing and administration details.
17. For DCC-2618 patients only, PK sampling will be performed at the following time points: Cycle 1 Day 1 pre-dose and 6 hours after dosing, Cycle 1 Day 15 pre-dose, and 2 and 6 hours after dosing, pre-dose at Day 1 of Cycles 2, 3 and Day 1 of every other cycle thereafter (e.g. Cycle 5, 7, 9, etc.), and at the EOT Visit. All pre-dose samples must be collected within 60 minutes before dosing and all post-dose samples must be collected  $\pm 30$  minutes of the nominal time point. An unscheduled PK sample may be taken at the time of onset of a new, suspected, treatment-related adverse event when requested by the Sponsor.
18. **South Korea Only:** Pharmacogenomics samples will not be collected.
19. Molecular pathology report with mutational status of KIT/PDGFR $\alpha$  must be available. Mutation status must be identified using a tissue based PCR/sequencing assay. Molecular pathology report with mutation status of KIT/PDGFR $\alpha$  must be provided to the Sponsor for review prior to randomization. If the molecular pathology report is not available or insufficient, an archival tumor tissue sample or fresh biopsy is required for mutation status confirmation at the central laboratory prior to randomization. Specific instructions will be provided in the Study Reference Manual.

21. All Patients (optional): Additional tumor tissue samples may be collected at the EOT visit and/or for patients undergoing medical procedures including resection of metastases while on study or for patients that have disease progression if the patient consents and these samples will be used for further molecular testing of the cancer while treated with study drug.
  22. Radiologic imaging must be performed within 21 days prior to the first dose of study drug. Radiologic imaging performed as standard of care prior to informed consent may be used as the Screening assessment as long as the imaging was performed within 21 days prior to the first dose of study drug. CT scans of the pelvis, abdomen, and chest will be performed at screening. Subsequently, CT scans of the pelvis and abdomen will be performed at Days 1 of Cycles 2-7, and Day 1 of every odd-numbered cycle thereafter (e.g. Cycles 9, 11, 13 etc.) and EOT visit. A scan at the EOT visit is not required if disease progression was previously confirmed by independent radiologic review or if less than 28 days have passed since the last scan was performed. CT scans of the chest will only be performed subsequently, if the patient had lung metastases at screening or in case of lung symptoms (per the Investigator's discretion). Radiologic imaging may be performed up to 7 days prior to the corresponding study visit or post dose at the study visit. Following Cycle 7 Day 1, any initial indication of a partial or complete response based on investigator assessment must be confirmed  $\geq 4$  weeks following initial response. MRI scans of the abdomen/pelvis and CT scan without contrast of the chest can be used for patients who are allergic to radiographic contrast media or at the Investigator's discretion based on the best interest of the patient after discussion with the Sponsor. Additionally, for patients whose local regulatory authority and/or ethics committee has not approved use of CT scans, MRIs may be used. For each patient, the same assessment technique must be used throughout their participation on study unless there is a safety risk as determined by the Investigator. Ultrasound scanning is not an acceptable substitute for CT scanning.  
Validation of No Disease Progression: If the independent radiologic reviewer validates that there is no disease progression per modified RECIST, the patient will continue to receive study drug. If the Investigator determines clinical progression based upon clinical deterioration and wishes to end treatment, a scan must be performed prior to treatment discontinuation. The scan must be submitted to for independent radiologic review. The basis for determination of progression due to clinical deterioration must be documented in the patient's source documents and electronic case report form. If the Investigator's assessment determines disease progression per modified RECIST, the Investigator should wait for confirmation from the independent radiologic review before discontinuing the patient from treatment. If the Investigator wishes to end treatment due to local progression, without confirmation of progression by independent radiographic review, or before the independent read results are available, the Investigator must reach out to the Sponsor Medical Monitor to discuss.
- 

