Dose:	
DCC-2618: 150 mg QD continuous dosing for 6 week (42 days) cycles.
 
Sunitinib: 50 mg QD in 6 week (42 days) cycles with 4 weeks continuous dosing followed by 2 week break. Dose modifications are allowed per approved package insert or institutional guidelines. Pharmacokinetic (PK)-guided dosing is not allowed. Every effort should be made to continue patients on the starting sunitinib dose regimen throughout the first cycle, unless toxicity mandates dose modification.

Route of Administration:	Oral

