#### 2.2.2. Other Secondary Objectives

- To assess the quality-of-life (QOL) during treatment as measured by:
  - EORTC QLQ-C30
  - Dermatology Life Quality Index (DLQI)
  - GP5 question from the FACT-G (burden of side-effects)
- To assess Time to Tumor Progression (TTP) by independent radiologic review
- To assess efficacy parameters, including disease control rate (DCR), PFS based on Investigator assessment, and efficacy based on Choi criteria by independent radiologic review
- To assess the PK/PD relationship of DCC-2618
- To compare the safety profile of DCC-2618 to the safety profile of sunitinib

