9.1.2. Study Drug Exposure in Sunitinib Arm

For sunitinib arm, treatment duration will be calculated as (last dose date - first dose date + 1 day)/30.4375 months.

The cumulative dose (mg) of sunitinib in a cycle is the sum of the actual dose levels that the patient received within the cycle (ie, total dose administered). Total cumulative dose of sunitinib will be calculated as the total amount of doses received on study.

RDI in a cycle will be calculated as (cumulative dose received in the cycle)/(50*7*4 mg)×100%.

Overall RDI will be calculated as (total cumulative dose received)/(Total number of cycles started*[50*7*4])×100%.

CONFIDENTIAL Page 24 of 29

Person year will be calculated as the sum of (last dose date before discontinuation treatment – first dose date + 1 day)/365.25.

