9.6. Vital Signs

Temperature, heart rate, respiratory rate, and blood pressure will be summarized overall by time point utilizing continuous descriptive statistics. In addition, the change from baseline will be summarized for continuous parameters. For categorical parameters, the number and percentage of patients with assessment will be displayed.

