9.7. Electrocardiograms

PR, QRS, QT, QTc (ie, QTcB and QTcF) and RR intervals and their change from baseline will be summarized for each treatment arm by scheduled visit. Patients will be categorized into >450, >480, or >500 ms per their maximum post-baseline absolute QTc interval and >30, or >60 ms per their maximum change from baseline QTc interval. Additionally, patients will be classified into the following categories: HR \le 50 bpm and/or decrease from baseline \ge 20 bpm; HR \ge 120 bpm and/or increase from baseline \ge 20 bpm; PR \ge 220 ms and/or increase from baseline \ge 20 ms; QRS \ge 120 ms. The number and percentage of patients in each category will be summarized for each treatment group.

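### On sunitinib's planned 4/2 schedule, every scheduled ECG and LVEF test before EOT, and every scheduled lab and vital-sign test from Cycle 3 until EOT, falls at the end of the drug-free break, and SAP 9.5 to 9.8 take no account of dosing phase

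*Protocol*

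**What the plan says.** The Protocol synopsis (Dose) gives ripretinib (DCC-2618) as "150 mg QD continuous dosing for 6 week (42 days) cycles" and sunitinib as "50 mg QD in 6 week (42 days) cycles with 4 weeks continuous dosing followed by 2 week break". Protocol 2.2.2 lists this among the other secondary objectives: "To compare the safety profile of DCC-2618 to the safety profile of sunitinib".

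The tests are placed by Protocol Table 1 and its notes:

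- **LVEF:** "An echocardiogram or MUGA will be performed at screening, Cycle 3 Day 1, and Day 1 of every third cycle thereafter". The same sentence goes on to add EOT and clinically indicated tests.
- **ECG:** Day 1 of every cycle and EOT. Protocol 6.11.4 requires the ECG before the dose.
- **Haematology, chemistry and vital signs:** Days 1, 15 and 29 of Cycle 1, Days 1 and 29 of Cycle 2, Day 1 only from Cycle 3, and EOT. Day 29 from Cycle 3 is a remote questionnaire.
- **All assessments** are predose unless otherwise stated (note 1). The EOT visit falls within 7 days of the last dose.

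The SAP summarises these data by visit or time point and by extremes. For vital signs (SAP 9.6): "Temperature, heart rate, respiratory rate, and blood pressure will be summarized overall by time point utilizing continuous descriptive statistics". For ECG (SAP 9.7): "Patients will be categorized into >450, >480, or >500 ms per their maximum post-baseline absolute QTc interval". SAP 9.5 adds the maximum CTCAE grade shift for labs. SAP 9.8 gives LVEF and its change from baseline. None of the four sections mentions where in the dosing cycle a value was taken.

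**The concern.** If one arm is always measured after a break and the other never is, a difference or similarity between arms mixes drug with dosing phase. A sunitinib effect on QTc, LVEF, blood pressure, blood counts or chemistry that fades during two weeks without dosing would be only partly visible at Day 1. By-visit means and QTc categories could then suggest that sunitinib is as safe as ripretinib on these measures, or safer, because of when it was measured. A reader of the clinical study report would not see this unless the tables showed it.

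**Working it through.** **Inputs.** Cycle structure: Protocol synopsis (Dose). Visit days and windows: Table 1. Fixed visit calendar during interruptions: Protocol 5.4. Horizons: the design medians of 6 months (sunitinib) and 9 months (ripretinib) in Protocol 9.1, and the 24.1-week median PFS for sunitinib in Protocol 1.4.

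**The plan's own figures.** 28 days on + 14 days off = 42 days. SAP 9.1.2 agrees: "RDI in a cycle will be calculated as (cumulative dose received in the cycle)/(50*7*4 mg" gives 50 × 7 × 4 = 1,400 mg per cycle, and 1,400 / 50 = 28 dosing days.

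**Days since last planned dose.** Study day of Cycle n, Day d = 42(n − 1) + d. The last planned sunitinib dose of Cycle n is on day 42(n − 1) + 28. All tests are predose.

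| Visit | Study day | Sunitinib 4/2: days since last dose | Ripretinib: days since last dose |
|---|---|---|---|
| C1D15 | 15 | 1 | 1 |
| C1D29 | 29 | 1 | 1 |
| C2D1 | 43 | 15 | 1 |
| C2D29 | 71 | 1 | 1 |
| C3D1 | 85 | 15 | 1 |
| C4D1 | 127 | 15 | 1 |
| C5D1 | 169 | 15 | 1 |
| C6D1 | 211 | 15 | 1 |
| C7D1 | 253 | 15 | 1 |

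Fifteen days since the last dose means 14 full drug-free days. With the ±3-day window on Day 1 the range is 12 to 18 days if dosing has not restarted. At C2D29 the latest visit is Day 32 of the cycle, which is 32 − 28 = 4 days after the last dose. A cut at 7 days therefore separates the two kinds of visit.

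**Scheduled visits after baseline and before EOT that follow the sunitinib break.** One month is 30.4375 days, as in the SAP.

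| Time on sunitinib | ECG | LVEF | Haematology, chemistry, vital signs |
|---|---|---|---|
| 24.1 weeks (168.7 days) | 3 of 3 | 1 of 1 | 3 of 6 |
| 6 months (182.6 days) | 4 of 4 | 1 of 1 | 4 of 7 |
| 9 months (273.9 days) | 6 of 6 | 2 of 2 | 6 of 9 |

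The lab and vital-sign visits outside the break are always C1D15, C1D29 and C2D29; there are none from Cycle 3. For ripretinib, no scheduled visit follows a planned break.

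**What EOT adds.** It is one visit per patient. It catches a recent dose when a patient stops during Days 1 to 28. It need not when progression is seen on a scan taken at the end of the break: imaging may be done up to 7 days before Day 1 (Days 36 to 43), while the EOT window after a Day 28 dose closes on Day 28 + 7 = 35.

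**Contrast within the SAP.** For the EORTC function scales and EQ-VAS, SAP 8.3.3 averages C2D29 with C3D1 and C5D29 with C6D1, so each phase contributes one value. Scheduled ECG and LVEF have no Day 29 counterpart, nor do labs and vital signs from Cycle 3.

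**The case against.** A reader might infer that the safety comparison as a whole measures sunitinib off drug and ripretinib on drug. The documents do not support that:

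- Adverse events are collected continuously in both arms, and Protocol 7.7.1 requires clinically significant ECG, lab and vital-sign findings to be recorded as adverse events.
- Every one of these tests is also scheduled at EOT. A patient who restarts on Day 1 while the independent read is awaited can have an EOT visit within days of a real dose.
- The maximum CTCAE shift draws on C1D15, C1D29 and C2D29 as well as EOT. The maximum QTc category can include EOT.
- Unscheduled tests are allowed. They are clinically triggered, however, and SAP 3.2 maps them to scheduled visits where possible, so an on-drug value may be filed under an end-of-break visit.
- The summaries are descriptive. Protocol 9.8.6 rules out formal testing for adverse-event rates, vital signs, echocardiogram/MUGA and labs.

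Two further readings also go too far. Ripretinib is not sampled at full exposure: tests are predose, and Protocol Table 4 gives a combined trough of 1,058 against a maximum of 1,680 ng/mL at 150 mg QD (1,058 / 1,680 = 63%). Nor can one say how much sunitinib effect is lost by Day 1, because the documents give no half-life and no recovery time for any of these measures. Ripretinib interruptions of up to 28 days and modified sunitinib schedules are both allowed, so the counts above are nominal.

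All of this stands and limits the point. It does not remove the confounding in the by-visit ECG and LVEF tables, or in the lab and vital-sign tables from Cycle 3.

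**Conclusion.** The point holds for a defined set of tables. On an unmodified 4/2 schedule, all scheduled ECG and LVEF tests between baseline and EOT, and all scheduled lab and vital-sign tests from Cycle 3 until EOT, are taken in the sunitinib arm after 14 planned drug-free days and in the ripretinib arm during continuous dosing. At 6 months that is 4 of 4, 1 of 1 and 4 of 7 visits. Arm and dosing phase are confounded there, and any reversible sunitinib effect is likely to be understated. Neither the size of the understatement nor its presence for a given measure can be derived from the documents.

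This rests on three assumptions: patients stay on 4/2, visits occur near their nominal days, and the summaries in SAP 9.5, 9.6 and 9.8 are shown by arm, as SAP 9.7 states for ECG. It does not follow that the comparative safety objective goes unanswered, or that the visit schedule must change. This is a presentational gap that the SAP can close at small cost.

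**What to change.** Change the SAP only, and keep every table now planned.

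1. In SAP 9.5 to 9.8, add a split of post-baseline ECG, LVEF, lab and vital-sign values by days since last dose, using recorded dose dates rather than nominal visits. A cut at 7 days or fewer versus more than 7 would serve. Apply it to the maximum QTc category and the maximum CTCAE shift as well.
2. Show C1D15, C1D29 and C2D29 as the like-for-like lab and vital-sign comparison, alongside the all-visit summary and not in its place. Used alone, those three visits would omit the off phase, which is part of the assigned regimen, and everything after Cycle 2.
3. Footnote the Day 1 ECG and LVEF comparisons as end-of-break values for sunitinib patients on 4/2, and state that similar or better QTc or LVEF safety for sunitinib will not be concluded from them alone.

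The cost is a few extra tables, with small cells for on-drug sunitinib ECG and LVEF. No new data should be needed, provided the dose records that feed SAP 9.1 are detailed enough to date the last dose before each test.

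Whether to move any ECG or LVEF test to the existing Day 29 site visits is a safety-monitoring decision for the sponsor and is not part of this fix. Separately, Table 1 marks study-drug administration on Day 29 without distinguishing the arms, although Day 29 is the first day of the break on 4/2; these passages should be reconciled.
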